#### Payment

Describe the incentives (monetary or other) being offered to subjects for their participation. If monetary compensation is offered, indicate the amount and describe the terms and schedule of payment. Please review [this guidance](#) for more information on payments to subjects, including restrictions and expectations.

Project START-C2H In-Jail Eligibility Screening, Consent, and Assessment: All participants who consent to participate and complete

the two in-jail assessments will receive \$25 for their time to complete the first assessment and \$10 to complete the second assessment.. This amount has been used previously by CARE2HOPE staff for a similar time commitment and is commensurate with the burden and not coercive in this context. As is currently approved by the UK IRB and Kentucky Department of Corrections for CARE2HOPE UG3 phase (Protocol #43520), participants can receive their incentive by staff depositing the money into their commissary account upon departure from the facility. Staff obtain a receipt for the deposit for record keeping. If the jail's policy is to withdraw jail fees from the commissary account (thereby creating a situation where participants may not directly receive their research incentives), the staff will deposit the funds in their in-jail phone account (if shielded from fees) or provided the incentive in the form of cash or gift card with their personal belongings upon release.

**Post-release Intervention and Data Collection:** Participants will be compensated \$25 for completion of 3-month and \$25 for completion of 6-month follow-up surveys. Participants who update or verify their locator information between the baseline and 3-month and between the 3-month and 6-month follow-up will receive \$10 each time (total of \$20). Additionally, participants who refer individuals to the study and who screen eligible, will be offered \$10 for each referral, up to 3 individuals (total of \$30). This incentive structure and amounts are consistent with the IRB-approved CARE2HOPE UG3 (Protocol #43520). These amounts are commensurate with other studies, and not coercive. Payments will be made in cash for surveys completed in-person. Payments will be made by mailed cash card (e.g., electronic Visa card) for surveys completed by phone. Payments for follow-up surveys completed in jail (i.e., if a person is re-incarcerated) will be made on their commissary account, in-jail phone account, or provided in form of cash or gift card with personal belongings upon release (depending on policy of jail, as described above).

#### COVID-19 Policies

**Pre-Release.** If surveys are completed in the jail via Zoom or by phone, the incentive cash card cannot be provided to the participant directly until in-person meetings resume. However, the individual will be offered two options to receive payment: the REHN will place the incentive amount on their commissary account using an online app available through the jail or the REHN will mail the card with the incentive amount after their release.

Participants recruited from the community will be compensated \$25 for Baseline Part 1, \$10 for Baseline Part 2, \$25 for the 3-month follow-up, and \$25 for the 6-month survey. Participants who update or verify their locator information between baseline and 3-month and between 3-month and 6-month follow-up will receive \$10 each time (total of \$20). Additionally, participants who refer individuals to the study and who screen eligible, will be offered \$10 for each referral, up to 3 individuals (total of \$30). Participants in the intervention arm only will be compensated \$15 for HIV and HCV home-based (self-test) testing (optional). The total amount a participant will be compensated will be \$120-\$150.

#### CQI

We will offer all categories of participants (pharmacists, REHNS and CARE2HOPE participants a \$30 Western Union card as a compensation for their time and effort.

#### Costs to Subjects

Include a list of services and/or tests that will not be paid for by the sponsor and/or the study (e.g., MRI, HIV). Keep in mind that a subject will not know what is "standard" – and thus not covered by the sponsor/study – unless you tell them.

Not applicable

#### Data and Safety Monitoring

The IRB requires review and approval of data and safety monitoring plans for greater than minimal risk research or NIH-funded/FDA-regulated clinical investigations.

- If you are conducting greater than minimal risk research, or your clinical investigation is NIH-funded, describe your Data and Safety Monitoring Plan (DSMP). [Click here for additional guidance on developing a Data and Safety Monitoring Plan.](#)
- If this is a non-sponsored investigator-initiated protocol considered greater than minimal risk research, and if you are planning on using a Data and Safety Monitoring Board (DSMB) as part of your DSMP, [click here for additional guidance](#) for information to include with your IRB application.

This research project involves non-exempt human subjects as defined by DHHS regulations. It is an NIH-Defined Phase IV Clinical Trial as defined by DHHS regulations outlined in 45 CFR Part 46 - that is, the intervention's effectiveness has already been established in a large group of people, and we are now testing its effectiveness in other populations (for details, see <https://www.nlm.nih.gov/services/ctphases.html> ). Therefore, the PIs will be responsible for developing and executing the Data and Safety Monitoring Plan (DSMP), including establishment of an independent DSMB for the study.

For all CARE2HOPE components, we will gather data in private spaces that reduce the risk that others will overhear data collection activities. Interviewer-administered surveys will be conducted using Questionnaire Development Software's CAPI program. This platforms allow surveys to be programmed and data to be entered by interviewers using a touchscreen laptop. Data are automatically password protected and are uploaded to a Data Warehouse on the HIPAA-compliant server at the UK Center on Drug and Alcohol Research (storefront staff and Emory-based team members can VPN into this server).

Similarly, electronic versions of the biologic test results and audio files from qualitative interviews will be stored in password-protected databases on the HIPAA-compliant server at the UK Center on Drug and Alcohol Research. Audio recorders will be wiped of audiofiles

after data have been uploaded to the server. Qualitative interviews will be recorded on recorders that can be password protected.

Each participant will receive a unique identifying number and all research data collection instruments will be identified by this number only. The master list matching identifiers to specific participants will be maintained in a double-password protected database on the secure HIPAA-compliant server at the UK Center on Drug and Alcohol Research. Research data will be reported in aggregate form only. Participants will not be identified by name in analytic data files.

All staff will sign a confidentiality agreement, stating that they will not disclose information about participants to others outside the study team.

Procedures for preventing and addressing breaches of confidentiality: If a breach is identified, the PIs will immediately inform the UK IRB; NIH will be informed as decided by the UK IRB. Next steps will depend on the nature of the breach. Examples of possible steps include: retraining staff in confidentiality protocols; firing a staff member for a serious violation or repeated minor violations, despite training; or informing UK IT of a threat to HIPPA protections.

**Potential Adverse Events Reporting Procedure and Database:** Adverse events (AEs) that may occur during data collection may include violation of confidentiality, discomfort due to assessment procedures, embarrassment in disclosing sensitive personal information, disclosure of information about current and/or intended physical harm to persons; current and/or intended abuse of children that would be reported to a child welfare agency; and/or an investigation of such allegations(s) that could ensue, dissatisfaction with the assessment procedures, and dissatisfaction with the intervention activities. Serious adverse events (SAE) may also occur in our study population of people who use drugs and could include infections, hospitalizations, overdose, and death. AEs and SAEs events following randomization will be recorded on an Adverse Events Log. All potential adverse events will be reviewed as to the assigned treatment group and further classified by severity (life-threatening, serious, non-serious) and expected vs. unexpected. Expected adverse events, determined by consensus with the DSMB, will be monitored at each enrolling site, reported to overseeing agencies as required by federal regulations and local requirements, and reviewed periodically by the independent DSMB.

Adverse events will be reported to the NIDA Project Officer in the annual progress report. This report will describe the event, when it occurred, the study arm of the participant, and the outcome/resolution. If there were no AEs, we will so state in the progress report.

SAEs will be reported to the NIDA Project Officer within 24 hours of the event by email. This notification will include a brief explanation of the SAE and when it occurred. Within 72 hours of the event, we will send a follow up email that describes the date of the event, what occurred, actions taken by project staff, planned follow up (if any), the intervention group/study arm of the affected participant, whether the event appears to be related to the intervention, and whether participant will continue in the study. We will create a standard form to use for these communications.

**Interim Analyses of Efficacy Data.** We have proposed interim analyses of Project START-C2H data after approximately 50% the Project START-C2H participants have been recruited. During the first DSMB meeting, convened in the pre-implementation phase for Wave 1, the DSMB will work with the study statistician to establish stopping rules for this study. If there are large differences in serious adverse events or outcomes in blinded group comparisons, the DSMB may request that the statistician present an unblinded analysis of interim results to the DSMB who will determine if these rules and met and if the study can continue.

**Trial stopping rules.** The DSMB will determine if we should stop the trial. The DSMB will meet during the pre-implementation phase for Wave 1 to determine stopping rules.

All AEs will be reported to NIDA at least once per year as a part of the annual progress report. This report will describe the event, when it occurred, the study arm of the participant, and the outcome/resolution. If there were no AEs, a statement that no AEs occurred will be included in the progress report or communicated to NIDA in writing.

SAEs will be reported to NIDA within 24 hours of the event by email. The notification will include a brief explanation of the SAE and when it occurred. A written follow up will be sent within 72 hours of the event. The written follow up will include information on the date of the event, what occurred, actions taken by project staff, planned follow up (if any), the intervention group/study arm of the affected participant, whether the event appears to be related to the intervention, and whether participant will continue in the study).

**Reporting of IRB actions to NIDA:** All IRB actions will be reported to NIDA. The IRB director will provide guidance as to whether the action is reported in the progress report, or more rapidly, following SAE protocols described above.

**Data Safety Monitoring Board (DSMB):** The DSMB will be convened prior to initiation of the trial and will decide stopping rules, review the final protocol and consent process prior to trial implementation, and will provide input and approval. DSMB activities will include reviewing emerging trial data, and making recommendations about the trial's conduct, including possibly stopping the trial. At the close of each meeting, the DSMB will make one of four recommendations: continue as is, continue but with specific modifications; stop temporarily until specific conditions are met; or terminate. The PIs will report DSMB activity as part of their annual project progress report to NIDA.

The DSMB will meet via teleconference to review protocol changes, data collection procedures, evaluate the benefit and risk ratio to participants, and review and approve the statistical analysis plan for the study. The DSMB will advise the PIs if a change in the protocol is warranted and at each visit, will formally vote to allow the study to continue. The DSMB may vote to discontinue the study due to safety concerns.

A report on DSMB meetings and activities will be sent to NIDA within a month after each DSMB meeting. The update will include the following: meeting dates (past and upcoming if known), meeting minutes or summary, current board membership, changes in

membership (if applicable), information about any new member(s) (if applicable) including statement that new members have no conflict of interest, and specific board recommendations regarding the research project (if any).

We will submit reports from the DSMB to the UK IRB at continuation review summarizing the annual meetings; the DSMB will elect a chair who will write those reports. The first meeting will be scheduled at the beginning of Year 1 of the UH3, before the trial begins. Annual meetings will be held thereafter, with a final report due in Year 3 of the UH3. The DSMB's responsibilities will be to create stopping rules, and monitor the trial's safety, efficacy, and statistical assumptions and analyses.

The DSMB members shall have no conflicts of interest and no DSMB member will have ties to any study center or study team member to ensure independence. Should a conflict arise, the DSMB will step down and be replaced. Our DSMB will meet in during the pre-implementation phase for the first Wave of counties, and will establish the frequency of subsequent meetings, with a frequency of no less than once per year.

[Back to Top](#)

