### Overview of START

START, in its original format, is a manualized, six-session individual-level intervention that evidence indicates reduces vulnerability to HIV and STIs among people who are returning to the community from correctional settings. START has been adapted over the last several months for use with individuals who have been released into the community after being involved with the criminal justice system (i.e. spending time in a correctional institution or on probation or parole). START originally was designed to have 6 sessions: two with inmates before release from jail and 4 in the community after release. The modified version of START consists of 4 intervention visits that all take place in the community.

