START core components: (1) Hold pre- and post-release program sessions with clients transitioning back to the community from a correctional setting; this component has been modified to include individuals who have been criminal justice involved in the last thirty days who are living in communities covered by our project; (2) Use a client-focused incremental risk reduction approach; (3) Use assessment & documentation tools to provide structure; (4) Hire program staff that are familiar with HIV/STIs/HCV prevention and with the specific needs of people being released; (5) Staff /client relationships must be maintained post-release; in the case of those individuals recruited from the community the relationship must be built and maintained in the community setting; (6) Conduct enrollment and schedule four intervention visits in the community over the span of 3 months that: a. give HIV/STI/HCV information; b. review client's HIV/STI/HCV risk; c. identify transitional needs; d. develop a personalized risk reduction and transitional plan; e. make facilitated referrals; (7) Schedule four post-release sessions, or for those enrolled in the community, post-enrollment sessions, to review and update the risk reduction/transitional plan(s) and provide facilitated referrals; (8) Provide fentanyl education, asking participants to watch a 4-minute educational video for FTS cited in previous research and available on YouTube at <https://www.youtube.com/watch?v=glovAAV-Amg>, assess fentanyl knowledge through a quiz (attached), and provide fentanyl test strips at the first post-release session or for those enrolled in the community, the first post-enrollment session; and, provide fentanyl test strips and condoms at each subsequent post-release session or for those enrolled in the community, post enrollment sessions; (9) Actively maintain contact with clients.

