#### Comparison Condition

We will initiate the comparison group in each county six months before the intervention begins. The current "treatment as usual" condition for most individuals, especially individuals not entering parole/probation supervision, is to provide no post-release services. Given the high risk of overdose post-release, we will conduct a pre-release overdose intervention with the comparison cohort. Individuals recruited in the community will receive overdose education during their baseline visit as well. Overdoses are not a primary study outcome, and it would be unethical to withhold overdose education from this cohort. Six months before the intervention starts in a county, REHNS will use the same pre-release recruitment, consent, and enrollment protocols (including eligibility criteria, except individuals must live in counties that are currently randomized to the comparison group) as proposed for the intervention condition. As with START's original evaluation, we will administer a single session, pre-release intervention for the comparison group; if someone is recruited in the community, they will receive this visit as well. Specifically, the comparison group participants will complete the a training with people demonstrating how to respond to an overdose and narration on preventing, recognizing, and responding effectively to an opioid OD, accompanied by information about Kentucky's Good Samaritan Law and Naloxone Access Law. REHNS will answer questions after the video. Individuals will receive a Community Resource Guide at this visit.

As in the intervention group, comparison group participants will complete assessments at pre-release (two sessions), for those recruited in the community this will happen at the REHNS office, and at 3 months and 6 months weeks post-release (post-enrollment for those recruited in the community). Surveys will be identical to those delivered to the intervention cohort, as will incentives. No interventions will be delivered at these follow up appointments. Retention efforts for comparison participants will be identical to those for intervention participants (described previously).

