#### COVID-19 Policies.

We will offer all participants in the intervention arm HIV and HCV testing. Research staff will perform testing as described above in the office. However, if a participant prefers, we will help them perform the test using a self-test kit, or we we will make a referral to a local health department.

HIV and HCV testing are only offered to participants in the intervention arm. Testing is offered in the local health departments through UK's Kentucky Income Reinvestment Program (KIRP) with UK staff based at the health departments. The Kentucky

Cabinet for Health and Family Services' Department for Public Health and UK established KIRP to improve health care delivery via disease education, prevention, treatment and professional services for persons living with HIV through collaborations with existing Ryan [name] HIV/AIDS funded programs and harm reduction programs at local health departments. Testing is offered through collaboration with the harm reduction programs.

For participants who prefer to test themselves, we will offer home-based (self-test)HIV and HCV testing and drug screening to be completed in-person at the study office. If the participant does not feel comfortable coming to the office or all research activities are remote only due to COVID-19 restrictions, we will offer to meet the participant at a mutually agreed-upon location or their home to complete home-based (self-test) HIV and HCV testing.

For home-based (self-test) HIV testing we will use FDA-approved OraQuick In-Home HIV Test (OraSure Technologies, Inc., Bethlehem, PA) that tests for HIV antibodies in human saliva (gum swab) with 91.67% sensitivity and 99.9% specificity, with results ready in 20 minutes. For home-based(self-test) HCV testing we will use EverlyWell HCV human antibody test (Everlywell, Inc., Austin, TX), which requires finger stick to obtain blood for a dry spot sample that will be mailed to a laboratory for processing. Both sensitivity and specificity for this test are above 99%. We will conduct saliva drug test using SalivaConfirm (TestCountry, San Diego, CA) drug screening kit that detects 10 types of illicit drugs in the sample in 10 minutes.

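### The plan sets no common way of finding serious adverse events, although scheduled contact and HIV/HCV testing differ by arm, so the between-arm comparison is open to detection bias

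*Combined protocol and SAP*

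**What the plan says.** The Data and Safety Monitoring section states that SAEs in this population "could include infections, hospitalizations, overdose, and death" and that "AEs and SAEs events following randomization will be recorded on an Adverse Events Log". It adds: "All potential adverse events will be reviewed as to the assigned treatment group". Its paragraph on interim analyses continues: "If there are large differences in serious adverse events or outcomes in blinded group comparisons, the DSMB may request" an unblinded presentation, to be judged against stopping rules that the DSMB will set. The section gives no question set, time points or sources for finding SAEs, and does not say whether survey answers feed the log.

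Contact differs by arm. On the intervention, Overview of START says: "The modified version of START consists of 4 intervention visits that all take place in the community". The section on CARE2HOPE's enhancements to START places them at a first community session and at months 1, 2 and 3. Comparison Condition puts that arm's post-baseline assessments "at 3 months and 6 months weeks post-release (post-enrollment for those recruited in the community", with no intervention delivered there. The modification of 6/28/22 drops the 6-month survey for new recruits. On testing, the HIV/AIDS Research section says: "HIV and HCV testing are only offered to participants in the intervention arm".

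Some things are shared. Comparison Condition makes surveys, incentives and retention efforts identical across arms, and Payment offers a paid locator update between baseline and month 3 without restricting it by arm.

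**The concern.** A between-arm count of SAEs measures harm only if an event has the same chance of being recorded in either arm. Here one arm meets a navigator repeatedly in the first three months and the other mainly meets survey staff at month 3. Infections are named among the SAEs without being limited to new, symptomatic or hospitalised ones, while the tests that could reveal them are offered in one arm only.

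At stake are the DSMB's reading of a large difference, its decision whether to ask for an unblinded analysis, and any SAE table reported by arm. Extra detection in the intervention arm could look like harm, or could mask a true excess in the comparison arm. The efficacy estimate is not affected.

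**Working it through.** The plan gives no SAE rate, capture probability or safety power, so there is no figure of its own to reproduce on this point.

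**Step 1. Contacts by arm**

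| | Intervention | Comparison |
|---|---|---|
| Scheduled post-baseline contacts to month 3 | first session, months 1, 2, 3: **4** | month 3: **1** |
| To month 6 | 5 | 2 |
| To month 6, where the 6-month survey is dropped | 4 | 1 |
| HIV/HCV testing offered | yes | no |
| Month-3 survey | identical | identical |

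The first session is placed at day 10 (10/30.4 = 0.33 months). This follows the follow-up provisions in the Prisoners section, which has staff meet participants within 10 days of release.

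**Step 2. Detection model.** Assumptions: equal true risk in both arms; events uniform over months 0 to 3; each later contact reveals an event independently with probability q; full attendance. The values of q are assumed.

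In the intervention arm, the share of events followed by 4, 3, 2 or 1 contacts is 0.33/3 = 0.110, 0.67/3 = 0.224, 1/3 and 1/3. The mean number of later contacts is (0.33 + 1 + 2 + 3)/3 = 2.1, against 1 in the comparison arm.

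- Intervention share detected: 1 − [0.110(1−q)⁴ + 0.224(1−q)³ + 0.333(1−q)² + 0.333(1−q)]
- Comparison share detected: q

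At q = 0.5 the bracket is 0.007 + 0.028 + 0.083 + 0.167 = 0.285. The intervention arm detects 0.715, and the ratio is 0.715/0.5 = 1.43.

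**Step 3. A locator contact in the comparison arm.** Suppose one contact at month 1.5 reveals SAEs as well as a visit does. The comparison share becomes 1 − [0.5(1−q)² + 0.5(1−q)]. At q = 0.5 this is 0.625, and the ratio is 0.715/0.625 = 1.14.

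| q | Ratio, scheduled contacts only | Ratio, comparison arm also has one locator contact |
|---|---|---|
| 0.3 | 1.67 | 1.24 |
| 0.5 | 1.43 | 1.14 |
| 0.7 | 1.23 | 1.07 |
| 0.9 | 1.07 | 1.02 |
| 1.0 | 1.00 | 1.00 |

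With 80% attendance at each contact, q is replaced by 0.8q. The scheduled-contact ratio then runs from 1.75 (q = 0.3) to 1.15 (q = 1.0), so incomplete retention leaves a gap even when every attended contact reveals every event.

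**Step 4. Scale in events.** Statistical Design and Power assumes 12 counties × 20 participants = 240, or 120 per arm if split equally. With an assumed true risk of 10% and q = 0.5, expected counts are 120 × 0.10 × 0.715 = 8.6 against 120 × 0.10 × 0.5 = 6.0. A two-proportion test at two-sided 0.05, ignoring clustering, would then fall against the intervention about 10% of the time, where 2.5% is nominal.

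**Step 5. Infections.** The section on the post-release, DOH-centered session has community recruits tested at the baseline visit, so a positive result there will mostly reflect existing infection. Counties are randomised before individuals enrol, so a log that opens at randomisation does not exclude it.

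**Step 6. Same source in both arms.** If only the identical month-3 survey feeds a comparison, each arm has one ascertainment point. The expected ratio is q/q = 1.00 for any q, given equal retention.

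**The case against.** The strongest reply is that the plan is silent on how events are found, and silence is not passive capture. A reader might infer that SAEs are logged whenever staff happen to hear of them; no section says so. The survey is identical in both arms, and the risk section shows that it asks about overdose, HIV and HCV, so it may feed the log. Timeline follow-back is used to improve recall. This stands: the documents support a missing rule, not a demonstrated bias.

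A reader might also infer that the comparison arm is reached only once before month 3. That holds for scheduled appointments only. Retention efforts are identical and a paid locator update falls in that interval. The Prisoners section (follow-up provisions) and the drug-screening paragraph of Data Collection also describe early contacts without naming an arm. These contacts shrink the gap. They close it only if capture at each contact is complete, and nothing says that locator contacts ask about SAEs.

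A third inference would count every positive study test as an SAE. With 120 intervention participants, 70–100% uptake and 20–60% HCV antibody prevalence, that gives 120 × 0.2 × 0.7 = 17 to 120 × 0.6 × 1.0 = 72 in one arm against none in the other. Uptake and prevalence are not in the documents, nothing makes a positive screen an SAE, and comparison participants can report HIV or HCV in the survey. Likewise, naloxone resupply need not reveal the participant's own overdose: kits may be used on others or lost.

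Finally, the DSMB's step is discretionary, the DSMB sets the stopping rules, and SAE reports state relatedness, so it can weigh contact intensity. That is true, but without a recorded source it has nothing to weigh it with. After month 3, comparison participants offered the intervention gain contacts while still belonging to their assigned group, which pulls the other way.

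**Conclusion.** The concern holds in a limited form. SAEs are compared by arm and the comparison can prompt an unblinded look, yet no common ascertainment is set while scheduled contacts by month 3 stand at 4 against 1 and testing is offered in one arm. The comparison is open to detection bias, probably against the intervention.

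The size cannot be known from the documents. It ranges from none, if month-3 capture and retention are complete, to roughly 1.1–1.7 fold under assumed detection probabilities of 0.9 down to 0.3, and to 1.00–1.24 if one locator contact reveals events equally well. These figures rest on equal true risk, events uniform over three months, independent detection at each contact and full attendance. They exclude infections found by testing. The documents do not support saying that the comparison is biased by a given amount.

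**What to change.** In the Data and Safety Monitoring section:

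- Keep the all-SAE table by arm, including all deaths, and find deaths from one named source applied identically in both arms.
- Add two fields to the log: source (survey, intervention session, naloxone resupply, third party) and date of discovery.
- Give the DSMB, beside that table, a between-arm table limited to events ascertained the same way in both arms: overdose and hospitalisation from the identical 3-month survey. The survey form is not shown, so if hospitalisation is not already asked, add the same item in both arms. Have the DSMB read any large difference against this table.
- List infections found only by study HIV/HCV testing separately, outside the between-arm SAE count.
- Start each participant's window at consent. This gives a usable time origin but does not by itself exclude baseline test results, so the separate listing is still needed.
- Reconcile the follow-up provisions in the Prisoners section and the 1-week drug screen in Data Collection with Comparison Condition on which arm has the early contacts.

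The cost is wording, two log fields, possibly one survey item, and one extra table. The common-source table has fewer events and covers survey responders only. It would miss deaths, fatal overdoses and events in people lost to follow-up, so it must supplement the all-SAE table and not replace it. Individual SAE reporting to NIDA is unchanged.
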